5.8 Sponsor Reporting Requirements

Depending on relevant local legislation or regulations, including the applicable US FDA Code of Federal Regulations, the EU Clinical Trials Directive (2001/20/EC) and relevant updates, and other country-specific legislation or regulations, the Sponsor may be required to expedite to worldwide regulatory agencies reports of SAEs, serious adverse drug reactions (SADRs), or suspected unexpected serious adverse reactions (SUSARs). In accordance with the EU Clinical Trials Directive (2001/20/EC), the Sponsor or a specified designee will notify worldwide regulatory agencies and the relevant IEC in concerned Member States of applicable SUSARs as outlined in current regulations.

Assessment of expectedness for SAEs will be determined by the Sponsor using reference safety information specified in the Investigator's brochure or relevant local label as applicable.

All Investigators will receive a safety letter notifying them of relevant SUSAR reports associated with any study IMP. The Investigator should notify the IRB or IEC of SUSAR reports as soon as is practical, where this is required by local regulatory agencies, and in accordance with the local institutional policy.

5.9 Concomitant Medication Assessments

All concomitant medications reported during the study period will be recorded and assessed for all subjects.

5.10 Removal of Subjects from the Trial or Study Drug

The subject may be withdrawn from the study for any of the following reasons:

- A protocol violation occurs
- A serious or intolerable adverse event occurs
- A clinically significant change in a laboratory parameter occurs
- The subject does not adhere to dosing schedules or specified evaluations are not completed
- The Sponsor terminates the study
- The Investigator determines a subject should not continue study treatment
- The subject requests to be discontinued from the study
- A stopping criteria is met

5.11 Appropriateness of Measurements

The PK/PD and safety assessments are standard in clinical trials of growth hormone replacement agents in adults.

6 STUDY ACTIVITIES

Study activities are described in Section 6.1 and Appendix 1.

6.1 All Subjects

6.1.1 Screening

Subjects will sign the study-specific consent in the presence of a study research health care professional familiar with the protocol and the process of providing informed consent. Subjects may undergo study specific Screening activities only after consent is provided and up to 30 days prior to enrollment (Day 1) in the study. For subjects who participated in a previous Versartis study, assessments from the previous somavaratan study may be used for entry into this study (if conducted within the previous 30 days). Subjects are considered enrolled in the study after providing written informed consent and fulfillment of the inclusion/exclusion criteria.

During the Screening period subjects will have the following procedures and activities performed:

1. Informed consent.
2. Verification of inclusion/exclusion criteria.
3. Medical history including documentation of Baseline signs and symptoms (ongoing observations documented using CTCAE V.4.0 grading scale).
4. Full physical exam.
5. Vital signs including respiratory rate, pulse rate, and systolic/diastolic blood pressure taken after 5 minutes' rest in a sitting position.
6. Body weight measured in light clothing and without shoes.
7. 12-lead ECG (new naïve to somavaratan subjects only, triplicate tracings required).
8. In new naïve to somavaratan subjects only, collection of blood samples for PD.
9. Serum pregnancy test for women of child bearing potential (Appendix 2). Urine test acceptable for subjects who participated in a previous Versartis study.
10. Collection of fasting blood samples for hematology, serum chemistry, lipid profile, glucose metabolism and thyroid function tests.
11. Adrenal stimulation testing (if subject is not on glucocorticoid replacement for adrenal insufficiency or if adrenal function has not been evaluated in the 3 months prior to Screening).
12. Urinalysis by urine Multistix® (or similar).

13. Recording of AEs using the CTCAE V.4.0 grading scale.

14. Recording of all concomitant medications.

6.1.2 Visit Day 1 Procedures

Subjects may undergo study specific Day 1 activities only after consent is provided and subject enrollment is approved by the Medical Monitor and subject number is assigned. For subjects who completed a previous Versartis study, the End of Study assessments from the previous somavaratan study may be used for entry into this study (if conducted within the previous 30 days). Assessments on Visit Day 1 to be obtained prior to dosing include:

1. Brief physical exam (brief, problem-specific exam may be performed for any reported AE at the discretion of the Investigator). Ongoing observations documented using CTCAE V.4.0 scale.
2. Vital signs including respiration, pulse rate and systolic/diastolic blood pressure taken after 5 minutes' rest in a sitting position.
3. Body weight measured in light clothing and without shoes.
4. Collection of pre-dose blood samples for PD (IGF-I and IGFBP-3) PK and immunogenicity
5. Urine pregnancy test.
6. Recording of AEs using the CTCAE V.4.0 grading scale.
7. Recording of all concomitant medications.
8. Somavaratan dose administered in clinic by a qualified health care professional.
9. Scheduling of next site visit.
10. Training on process for study drug storage, preparation, administration and how to document dosing information into the IWRS system.

6.1.3 First Month Procedures

All subjects will begin twice-monthly somavaratan treatment during the first month with in clinic study drug administration required on Day 1 and Day 16. Twice-monthly somavaratan dosing should occur every 15 days \pm 2 days. Blood samples will be obtained on Day 8, 16, and 23 for PK and PD assessment. Blood samples on Days 1 and 16 are intended as trough samples and should be collected pre-dose. Blood samples on Day 8 and 23 are intended as peak samples and may be collected at the subject's home by an at-home health care provider. All blood sample collections should occur within \pm 1 day of the target collection day, with trough samples always collected pre-dose. In new naïve to somavaratan treatment subjects only, 12-lead ECGs shall be collected 3 days (\pm 1 day) after Day 1 dosing during the first Month (triplicate tracings).

Recording of concomitant medications, adverse events and study drug administration will be performed for all subjects.

6.1.4 Monthly Visits During Titration

During monthly dose titration in clinic study drug administration will be required on Day 1 of each month. Twice-monthly somavaratan dosing should occur every 15 days \pm 2 days. At home dosing is permitted for the Day 16 injection. Blood samples will be collected on Days 1 and 8 for PK and PD assessment. Blood samples on Day 1 are intended as trough samples and should be collected pre-dose. Blood samples on Day 8 are intended as peak samples. Blood sample collection on Day 8 may be conducted at the subjects' home by an at-home health care provider. All blood sample collections should occur within \pm 1 day of the target collection day, with trough samples always collected pre-dose. Subjects will return to the site at the end of each month during titration for an assessment and collection of blood samples and somavaratan dosing. Assessments to be obtained on Day 1 of each month during titration and prior to dosing include:

1. Brief physical exam (brief, problem-specific exam may be performed for any reported AE at the discretion of the Investigator). Injection sites will be inspected at all visits.
2. Vital signs including respiratory rate, pulse rate, and systolic/diastolic blood pressure taken after 5 minutes' rest in a sitting position.
3. Body weight measured in light clothing and without shoes.
4. In new naïve to somavaratan treatment subjects only, 12-lead ECGs shall be collected 3 days (\pm 1 day) after the Month 4 Day 1 dosing.
5. In new naïve to somavaratan treatment subjects only, collection of pre-dose blood samples for immunogenicity (ADA) at the Month 1 visit (approximately 30 days after Day 1).
6. Recording of AEs using the CTCAE V.4.0 grading scale.
7. Recording of all concomitant medications.
8. Somavaratan dose administered in clinic by a qualified health care professional.
9. Scheduling of next site visit.
10. Dispense study drug for subsequent doses until next clinic visit.

6.1.5 Quarterly Visits: Visit Month 3, 6, 9 and 12 Procedures

Subjects will return to the site at the end of Months 3, 6, 9 and 12 (\pm 3 days) for an assessment and collection of blood samples. Assessments on Visit Months 3, 6, 9 and 12 include:

1. Physical exam.

2. Vital signs including respiratory rate, pulse rate, and systolic/diastolic blood pressure taken after 5 minutes' rest in a sitting position.
3. Body weight measured in light clothing and without shoes.
4. Collection of pre-dose blood samples for PK and PD (IGF-I, IGFBP-3).
5. Additional PK and PD samples will be drawn 7 days after dosing (Day 8 \pm 1 day).
6. Collection of pre-dose blood samples for immunogenicity (ADA).
7. Collection of fasting blood samples for hematology, serum chemistry, lipid profile, glucose metabolism and thyroid function tests.
8. Urinalysis by urine Multistix® (or similar).
9. Urine pregnancy test for women of child bearing potential (Appendix 2).
10. Recording of AEs using the CTCAE V.4.0 grading scale.
11. Recording of all concomitant medications.
12. Somavaratan dose may be administered in clinic by a qualified health care professional.
13. Dispense study drug for subsequent doses.
14. Scheduling of next site visit (for the subsequent quarter if the subject is on maintenance dose or the subsequent month if further dose adjustment is necessary).

6.1.6 Subsequent Years of Quarterly Visits

After completion of the first year of treatment, subjects will return to the site for quarterly visits (Months 15, 18, 21, etc. (\pm 3 days) for an assessment and collection of blood samples.

Assessments at these visits include:

1. Physical exam.
2. Vital signs including respiratory rate, pulse rate, and systolic/diastolic blood pressure taken after 5 minutes' rest in a sitting position.
3. Body weight measured in light clothing and without shoes.
4. Blood samples collected every 6 months (e.g., Month 18, Month 24, Month 30, etc.) for:
 - a. Pre-dose blood samples for PK and PD (IGF-I, IGFBP-3).
 - b. PK and PD samples will be drawn 7 days after dosing (Day 8 \pm 1 day).
 - c. Pre-dose blood samples for immunogenicity (ADA).
 - d. Fasting blood samples for hematology, serum chemistry, lipid profile, glucose metabolism and thyroid function tests.
5. Urinalysis by urine Multistix® (or similar).

-
6. Urine pregnancy test for women of child bearing potential (Appendix 3).
 7. Recording of AEs using the CTCAE V.4.0 grading scale.
 8. Recording of all concomitant medications.
 9. Somavaratan dose may be administered in clinic by a qualified health care professional.
 10. Scheduling of next site visit.
 11. Dispense study drug for subsequent months.

6.1.7 Termination Visit

For subjects who terminate their participation in this study, the following assessments should be performed (not required for any assessments performed within the prior 14 days):

1. Physical exam.
2. Vital signs including respiratory rate, pulse rate, and systolic/diastolic blood pressure taken after 5 minutes' rest in a sitting position.
3. Body weight measured in light clothing and without shoes.
4. Collection of blood samples for PK (somavaratan plasma concentration) and PD (IGF-I, IGFBP-3).
5. Collection of blood samples for immunogenicity.
6. Collection of fasting blood samples for hematology, serum chemistry, lipid profile, glucose metabolism and thyroid function tests.
7. Urinalysis by urine Multistix® (or similar).
8. Urine pregnancy test for women of child bearing potential
9. Recording of AEs using the CTCAE V.4.0 grading scale.
10. Recording of all concomitant medications.

6.1.8 Follow Up Procedures

For subjects who terminate the study at any time, follow up should be conducted 60 days (\pm 3 days) after their final study dose. This may be conducted in clinic or by telephone contact and will include the collection of adverse events and concomitant medications. Subjects with an ongoing AE will be followed-up until the AE is resolved or stable. Subjects may be requested to return to the clinic approximately 3 months after study discontinuation for safety evaluation and blood sample collection.

7 QUALITY CONTROL AND ASSURANCE

This study will be conducted in accordance with the Food and Drug Association (FDA) Good Clinical Practice (GCP) and the International Conference on Harmonisation (ICH) consolidated guideline (April 2011). These guidelines include:

21 Code of Federal Regulations (CFR) parts 11, 50, 54, 56, 312 and 314

ICH E2a & ICH E6 (R1)

7.1 Adherence to the Protocol

The Principal Investigator and all personnel involved with the conduct of the study agree to adopt all reasonable measures to record data in accordance with the protocol. Under practical working conditions, however, some minor variations may occur due to circumstances beyond the control of the Investigator(s). All such deviations will be documented in the study records, together with the reason for their occurrence; where appropriate, deviations will be detailed in the clinical study report and provided in a timely manner to the Sponsor, Sponsor's designee and research site Institutional Review Board (IRB) or Independent Ethics Committee (IEC) per IRB/IEC guidelines.

Quality assurance audits of Investigator sites, CRO, and Sponsor study practices/procedures may occur. Any findings from quality assurance audits related to the study will be reported to the Medical Monitor and Study Director.

8 PLANNED STATISTICAL METHODS

8.1 General Considerations

This section presents a brief summary of the planned statistical analyses. A statistical analysis plan that describes the details of the analyses to be conducted will be finalized prior to database lock and un-blinding.

All summaries will be presented by cohort.

Summary statistics will be provided for the variables described below as follows. For continuous variables, these statistics will include the number of subjects, mean, standard deviation (SD), median, minimum, and maximum. For categorical variables, these statistics will include the number and percentage of subjects in each category.

The last observation obtained prior to the first dose in the current study will be used as the Baseline value for calculating change from Baseline.

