Downward Dose Titration		
IGF-I at Day 8	Cohort 1	Cohort 2
0 to 2.0 SDS	No change in dosing	No change in dosing
2.01 to 3.0 SDS	4 mg dose decrement	4 mg dose decrement
Greater than 3.0 SDS	10 mg dose decrement	10 mg dose decrement
Upward Dose Titration ¹		
IGF-I at Day 8	Cohort 1	Cohort 2
-1.0 to 0 SDS	4 mg dose increment	10 mg dose increment
Less than -1.0 to -2.0 SDS	10 mg dose increment	20 mg dose increment
Less than -2.0 SDS	20 mg dose increment	40 mg dose increment

1: Maximum allowable dose is 250.0 mg

DURATION OF TREATMENT

Subjects may continue on somavaratan treatment until the product is commercially available in their country or until the study is discontinued by the sponsor.

CRITERIA FOR EVALUATION – SAFETY

The following evaluations will be performed to assess study eligibility and safety:

1. Physical examination including injection site(s) evaluation.
2. Vital signs including sitting blood pressure, pulse rate, temperature and respiratory rate.
3. Laboratory tests: IGF-I, complete blood count, chemistry, fasting plasma glucose and insulin, hemoglobin A1c, thyroid function tests (Free T4 and TSH), pregnancy testing (for women of childbearing potential), lipid profile, ECGs (new subjects only), and screening anti-drug antibodies (ADAs).
4. Adverse events (AEs)
5. Concomitant medications (CMs)

Safety monitoring will continue up to approximately 60 days after a subject's final dose of somavaratan.

CRITERIA FOR EVALUATION – PHARMACODYNAMICS

Pharmacodynamic (PD) parameters include values of IGF-I and IGFBP-3. During month 1 of treatment, subjects will have IGF-I and IGFBP-3 measured every week (Day 1, Day 8, Day 16 and Day 23). After the first month and during the rest of the Titration Period, subjects will have IGF-I values measured at Day 1 (pre-dose, trough) and 7 days after dosing (Day 8, peak) of each month. During maintenance dosing PD parameters will be measured at Day 1 (pre-dose, trough) and 7 days after dosing (Day 8, peak) every three months for one year, and then every six months thereafter. Additional blood sample collection for IGF-I measures may be needed if previously stabilized subjects require further dose adjustments.

CRITERIA FOR EVALUATION – IMMUNOGENICITY

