Immunogenicity will be assessed by screening for anti-drug antibodies (ADAs) at baseline and every 3 months during the first year and every 6 months thereafter. ADAs will be measured on blood samples collected at troughs (pre-dose). Testing will follow a tiered approach consisting of screening, confirmation, titration, and additional characterization of confirmed ADA positive samples.

STATISTICAL METHODS

Safety data will be listed by subject and summarized by cohort using frequencies or descriptive statistics. All subjects who receive at least one dose of somavaratan will be included in the safety analysis. Summaries of all adverse events (AEs), serious adverse events (SAEs), and incidence of Grade 3 or 4 adverse events will be classified according to severity and relationship to study drug.

No formal hypothesis testing is planned for this extension study.

For continuous variables, descriptive statistics will include the number of subjects, mean, standard deviation (SD), median, minimum, and maximum. For categorical variables, descriptive statistics will include the number and percentage of subjects in each category.

Summaries of subject disposition, demographics, disease characteristics, and exposure and response to dosing of study medication will be provided.

Somavaratan ADAs will be summarized descriptively.

AEs, PK, and PD will also be descriptively summarized by ADA subgroup (positive, negative) to assess potential effects of ADA positivity.

TABLE OF CONTENTS

APPROVAL/SIGNATURE PAGE: SPONSOR AND CONTRACT RESEARCH ORGANIZATION	2
SYNOPSIS: PROTOCOL 15VR8.....	3
LIST OF ABBREVIATIONS AND DEFINITIONS OF TERMS.....	15
1 INTRODUCTION	22
1.1.1 Adult Growth Hormone Deficiency.....	23
1.1.2 Pediatric Growth Hormone Deficiency	24
1.1.3 Summary of Clinical Experience	26
2 STUDY OBJECTIVES.....	28
2.1 Primary Objective.....	28
2.2 Secondary Objectives.....	28
3 INVESTIGATIONAL PLAN.....	29
3.1 Overall Study Design and Plan.....	29
3.2 Rationale for Study Design.....	31
3.3 Dose Selection	31
3.4 Study Duration and Dates.....	32
3.5 Safety Review and Stopping Rules.....	32
3.5.1 Stopping Rules.....	32
STUDY POPULATION SELECTION	33
3.6 Study Population.....	33
3.7 Inclusion Criteria:	33
3.8 Exclusion Criteria:	34
3.9 Subject Withdrawals and Replacements.....	35
4 STUDY TREATMENT(S).....	36
4.1 Description of Treatment(s).....	36
4.1.1 Somavaratan Treatment	36
4.2 Treatments Administered.....	36
4.3 Selection and Timing of Dose for Each Subject.....	37

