Study visits/blood sample collections will occur every week during the first month of the study, followed by monthly clinic visits until the subject has reached maintenance dose. Once maintenance dose is achieved, in clinic visits will occur quarterly during the first year. Although quarterly visits will continue throughout the study, after the first year blood samples will be collected every 6 months, with intervening visits used for brief physical exams and collection of AEs and concomitant medications.

In current clinical practice with daily rhGH products, individualized dose titration is the standard of care. Daily rhGH doses are titrated to achieve normalization of IGF-I (the primary PD parameter) without jeopardizing safety. Each patient may have different IGF-I and safety

responses to daily rhGH treatment, especially with regards to potential adverse events such as edema. The IGF-I response to rhGH depends on many factors. One of the mostly recognized is the exposure to estrogens, in particular oral estrogens, which confers relative resistance to rhGH. Consequently, subjects will be stratified into the following two cohorts:

- Cohort 1: adults with GHD irrespective of age and gender will receive a starting dose of 20 mg twice-monthly
- Cohort 2: women receiving oral estrogen will receive a starting dose of 40 mg twice-monthly

Subjects entering the study currently receiving daily rhGH treatment must have discontinued rhGH for a minimum of 14 days prior to initiating treatment with somavaratan. Additionally, these subjects must have a baseline IGF-I SDS ≤ 0 .

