8.3 Demographics and Baseline Characteristics

Demographic and Baseline characteristics (including age, gender, race, weight, height, BMI, Baseline IGF-I level and IGF-I SDS) will be summarized by cohort and for the overall population using descriptive statistics.

Medical history and clinical laboratory tests results will be listed.

Prior and concomitant medications will be summarized by cohort and by the number and percentage of subjects taking each medication.

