8.4 Objectives

The primary objective of this study is:

- To evaluate the safety of somavaratan during long-term treatment in adults with GHD

The secondary objectives of this study are:

- To evaluate the dose (starting and maintenance) and the dose titration plan of twice-monthly somavaratan during long-term treatment
- To evaluate the immunogenicity of somavaratan during long-term treatment in adults with GHD by detection and characterization of anti-somavaratan antibodies (anti-drug antibodies, ADAs)

- To evaluate pharmacodynamic responses (IGF-I, IGFBP-3) during long-term somavaratan treatment

Somavaratan ADAs will be summarized descriptively.

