8.5 Safety

Safety analyses will be conducted on the safety population and will be summarized by cohort. Safety variables include AEs, clinical laboratory values, vital signs, and physical examination results.

AEs will be coded using MedDRA and will be summarized using the coded terms. Summaries of all treatment emergent adverse events (TEAEs), serious adverse events (SAEs) and Suspected, Unexpected Serious Adverse Reactions (SUSARs) will be presented. The incidence of CTCAE V.4.0 Grade 3 or 4 adverse events will be classified according to severity and relationship to study drug.

Observed and change from Baseline values for laboratory safety panels and vital signs will be summarized using descriptive statistics. Laboratory results will also be summarized and presented as shifts from Baseline.

No formal inferential analyses will be conducted for safety variables.

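### By-cohort tables, on the more natural reading, mix fixed-dose starters with half-dose rollovers and so would not isolate the response to the twice-monthly starting dose

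*Combined protocol and SAP*

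**What the plan says.** **Grouping.** Section 8.1: "All summaries will be presented by cohort". Section 8.5: "Safety analyses will be conducted on the safety population and will be summarized by cohort". Section 8.2 defines a single population, everyone given any study drug. Two other groupings appear. Section 8.3 adds an overall column for demographics and baseline, which "will be summarized by cohort and for the overall population using descriptive statistics". The Synopsis (Statistical Methods) adds antibody status: "AEs, PK, and PD will also be descriptively summarized by ADA subgroup (positive, negative").

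**Cohorts.** Section 3.1: "Consequently, subjects will be stratified into the following two cohorts". Cohort 2 is women on oral estrogen and Cohort 1 is everyone else, with fixed starting doses of 40 mg and 20 mg. The Synopsis and Sections 3.1 and 4.2 say that new subjects are assigned to a cohort. Rollovers, and subjects already dosed once-monthly in this study, move to half of their current dose.

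**Objective.** Section 8.4 repeats a secondary objective: "To evaluate the dose (starting and maintenance) and the dose titration plan of twice-monthly somavaratan during long-term treatment". The only analysis sentence in that section concerns antibodies. The Synopsis also promises a general summary of exposure and of response to study-drug dosing. On first-month sampling it says "subjects will have IGF-I and IGFBP-3 measured every week (Day 1, Day 8, Day 16 and Day 23").

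**Baseline.** Section 8.1: "The last observation obtained prior to the first dose in the current study will be used as the Baseline value".

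**The concern.** Whether 20 mg (or 40 mg) twice-monthly is a suitable start is answered by subjects who actually start on it without earlier somavaratan. Rollovers differ in three ways: their first twice-monthly dose is set by their own history, they have been exposed before, and they enter only if they tolerated the drug and met no stopping criterion (Section 3.7). If both groups share a column, a poor first response in new subjects can be diluted by rollovers, or a good one obscured.

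Section 4.2 lets the sponsor change starting doses and the titration plan on data from this study, and Section 8.7 allows periodic analysis for that purpose. Neither gives a grouping for that review.

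**Working it through.** The plan gives no figure for this point. The check is a reading of who falls in each column, then arithmetic on how far a combined rate can drift.

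**1. Who is in a cohort column?**
- For pooling: Section 3.1 stratifies subjects without limiting this to new ones. Section 4.2 applies the half-dose transition to rollovers whatever their cohort, which implies that they have one. All subjects titrate by Table 2, whose upward steps differ by cohort, so each subject needs a cohort to be dosed.
- Against: the sentences that assign subjects to cohorts name only new subjects, and Table 1 ties each cohort to a fixed starting dose.
- Pooling is the more natural reading, but rollover placement is not stated.

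**2. Do the groups start alike?** A new Cohort 1 subject starts at 20 mg. The example in the amendment rationale is a rollover on 54 mg once-monthly: 54/2 = 27, rounded down to 26 mg twice-monthly.

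**3. How large a share are new subjects?** Inputs: about 40 new subjects and at most 250 in total (Section 3.1); 36 Phase 2 subjects with a first-dose result and 29 with five doses (amendment rationale). Taking 29 or 36 as the number of rollovers is an assumption. Forty is treated as the ceiling for fixed-dose starters: the rationale says up to 40, and some may have entered under Version 1.

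**4. How far can the combined rate move?** Combined = (40 × new rate + R × rollover rate) / (40 + R), where R is the number of rollovers and the rate is the share above 2.0 SDS at first Day 8. The rates are illustrations, with equal mixing in both cohorts assumed. The 55% is the Phase 2 fifth-dose figure (16/29 = 55.2%), on once-monthly dosing before halving, so it is an upper case.

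| R | New share | New 10%, rollover 0% | 10%, 10% | 10%, 55% | 30%, 10% |
|---|---|---|---|---|---|
| 29 | 40/69 = 58% | 5.8% | 10.0% | 28.9% | 21.6% |
| 36 | 40/76 = 53% | 5.3% | 10.0% | 31.3% | 20.5% |
| 210 | 40/250 = 16% | 1.6% | 10.0% | 47.8% | 13.2% |

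In reverse, with R = 36 and a combined 30%, the rollover rate is (0.30 × 76 − 40 × new rate)/36. A new rate of 10% gives (22.8 − 4)/36 = 52%. A new rate of 50% gives (22.8 − 20)/36 = 8%. Both fit the same table entry. Equal rates give no distortion.

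**5. What would a separate table give?** Exact (Clopper-Pearson) 95% limits are the 0.025 quantile of Beta(x, n − x + 1) and the 0.975 quantile of Beta(x + 1, n − x). At an observed 10%:
- 4/40: 2.8% to 23.7%
- 3/30: 2.1% to 26.5%
- 2/20: 1.2% to 31.7%
- 1/10: 0.3% to 44.5%

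**6. What does the baseline rule measure?**
- New subjects: a value before any somavaratan, with screening IGF-I SDS at or below 0 (Section 3.7).
- Rollovers: a value after earlier exposure, with no such limit, possibly taken from the previous study's last visit (Section 6.1.2).
- Subjects dosed once-monthly here under Version 1: a value before those doses, so change from baseline and adverse-event counts span two regimens.

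**The case against.** The strongest reply is that cohorts may cover new subjects only, in which case the by-cohort tables already isolate the new entrants. The assignment sentences support that, and it cannot be ruled out. But rollovers would then have no column under a rule that covers all summaries, so placement needs stating on either reading.

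Second, Section 8.1 calls itself a brief summary and leaves detail to an SAP that is not part of the supplied text. By cohort sets a layout and does not forbid a further split, and safety data are also listed by subject. This stands: the limit is on tables built as written, not on the data. The reply is weaker on timing. Section 8.1 finalizes the SAP before database lock, while Section 9.10 says before enrollment but modifiable until lock. The study is open-label, rollovers are already in it, and periodic looks are allowed, so a grouping chosen late could follow the results.

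Third, the amendment rationale looked at first-dose, later-dose and rollover data separately, so the sponsor may well do so again. That is fair: nothing confines dose review to combined tables, and the masking above is a possibility rather than a prediction.

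A reader might infer that the baseline rule itself makes the starting dose unreadable. It does not. It pools no one, and the starting dose is judged on absolute Day 8 IGF-I SDS against 0 to 2.0. For trough IGF-I the rationale reports values similar to those before any exposure, so even the baseline shift there may be small.

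**Conclusion.** The point holds in limited form. On the more natural reading, the planned columns combine naive fixed-dose starters with half-dose rollovers, and no table in these documents isolates the starting-dose response. The only planned summary near it is the generic one of exposure and response to dosing. The size cannot be known in advance: new subjects may be 16% to 58% of a combined table, and distortion runs from none (equal rates) to large (10% shown as 47.8% in the extreme illustration). The baseline and regimen issue is separate and falls mainly on safety and change-from-baseline tables.

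Two stronger readings are not supported. One is that the objective cannot be evaluated: first Day 8 IGF-I is collected in all subjects, so a split is possible. The other is that earlier once-monthly data obscure the starting-dose result: the objective is confined to twice-monthly dosing.

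Severity is minor to moderate, since this is a descriptive secondary objective in a study with no hypothesis testing.

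**What to change.** In Sections 8.1 and 8.4, or in the SAP:

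1. State how rollovers are placed in cohorts. Within each cohort, show new and rollover subjects separately, plus an overall column.
2. Summarize the starting dose only in somavaratan-naive subjects whose first dose was the Version 2 fixed dose: the proportion with first Day 8 IGF-I above 2.0 SDS and above 3.0 SDS, each with an exact 95% interval.
3. Report once-monthly and twice-monthly periods separately, assigning each event and value to the regimen at the time. For subjects switched within 15VR8, add a baseline at the first twice-monthly dose.

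The cost is wording and extra table columns. Items 1 and 2 need no new data. Item 3 uses the last value before the switch; the Version 1 visit schedule is not in the documents, so how recent that value is should be checked. The downside is small cells and wide intervals, above all for new women on oral estrogen.

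As a separate matter, the minimum rollover dose for women on estrogen is stated differently in the Synopsis, the amendment rationale and Section 3.1 than in Sections 4.2 and 5. Those passages must be reconciled.
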